3.1 OVERVIEW

This is a phase I, randomised, double-blind, placebo-controlled study to investigate the safety, tolerability, and PK of AX-158 in healthy male participants following single (Part A) and multiple (Part C) ascending doses including food effect (Part B).

The study will be conducted in three parts:

Part A

Part A (SAD) will enrol up to 8 participants per cohort randomised (3:1) to receive AX-158 or placebo. Part A will follow a single ascending dose (SAD) design with all participants receiving one dose of AX-158 (or placebo) in the fasted state.

This part will be conducted in up to 34 participants (8 participants in cohorts 1 and 5, 6 participants in cohorts 2, 3 and 4). An additional two cohorts of up to eight (8) participants each (up to 16 additional participants total) may be investigated if required.

Part B

Part B (Food Effect) will be conducted in up to 8 participants in a cross-over manner; each participant will receive AX-158 in the fed and fasted state.

This part will be conducted in up to 8 participants in a cross-over manner.

Part C

Part C (MAD) will enrol up to 8 participants per cohort randomised to (3:1) to receive AX-158 or placebo. Part C will follow a multiple ascending dose (MAD) design with participants receiving AX-158 (or placebo) once daily for 10 consecutive days, in a fed or fasted state (depending on the outcome of the Part B (Food Effect)). Doses, dosing duration and dose regimen (i.e., q.i.d., b.i.d., t.i.d.) of AX-158 and matching placebo for Part C may be modified based on all available safety, tolerability, and PK data and applied to additional MAD cohorts.

This part will be conducted in up to twenty-four (24) participants (3 cohorts of up to 8 participants). An additional two cohorts of up to eight (8) participants each (up to 16 additional participants total) may be investigated if required.

Duration of study:

- Part A: approximately 6 weeks for each individual (from the screening to post-study follow-up).
- Part B: approximately 8 weeks for each individual (from the screening to post-study follow-up).
- Part C: approximately 7 weeks for each individual (from the screening to post-study follow-up).

A review of safety data and available preliminary PK data will be conducted by the DERC (Dose Escalation Review Committee). Following DERC review of data from Part A, the dose for participants in Part B will be determined. Following DERC review of data from Part B, the dose for participants in Part C will be determined, and cohorts in Part C may be administered AX-158 under fasted or fed conditions as deemed appropriate, pending DERC determination of any appreciable impact of food on the absorption, distribution, metabolism, and excretion (ADME) of AX-158.

3.2 INCLUSION AND EXCLUSION CRITERIA

To be eligible for inclusion into this study, each subject must fulfil all inclusion criteria and not violate any exclusion criteria (for the protocol under which they are entered) during screening prior to randomisation. Details of the inclusion and exclusion criteria are presented within the protocol (section 10.5).

3.3 STUDY TREATMENT

For Part A (SAD), 5 planned cohorts of 8 subjects (with an option to include up to 2 additional cohorts) will receive the following in accordance with the randomisation schedule:

- a single dose of AX-158 capsules (6 subjects)
- matching placebo (2 subjects)

The IMPs will be administered fasted with 240 ml water.

For Part B (Food Effect), 1 cohort of 8 subjects will receive a single dose of AX-158 capsules in either the fed or fasted state over 2 periods (1 per period) in accordance with the randomisation schedule.

For Part C (MAD), 3 cohorts of 8 subjects (with an option to include up to 2 additional cohorts) will receive the following in accordance with the randomisation schedule:

- AX-158 capsules for 10 days (6 subjects)
- matching placebo for 10 days (2 subjects)

The IMPs will be administered fasted with 240 ml water.

If a food effect is observed in Part B, cohorts in Part C may be dosed with a standardised meal.

For Part A (SAD) and Part C (MAD), a dose leader design will be implemented with 2 participants being dosed on the first dosing day of each cohort. Of these 2, 1 will be on active drug and 1 on placebo.

3.4 STUDY TIMEPOINTS

3.4.1 Schedule of Study Procedures

Part A

Visits ^{1,2}	Screening	Treatment Period														Follow up		
		In-house																
Days	Day - 28 to -2	Day - 1	Day 1										Post-Treatment 1 (Day 2)		Post-Treatment 2 (Day 3)		Post-Treatment 3 (Day 4)	
Time (h)			Pre-Dose	0	0.5	0.75	1h	2h	3h	4h	6h	8h	12h	24h	36h	48h	72h	
Informed Consent	X																	
Inclusion/Exclusion ³	X	X	X															
Demographics	X																	
Height/Weight/BMI ⁴	X	X																
Medical History & Concurrent Conditions	X																	
Virology Tests (HIV, HBsAg, HCV)	X																	
Drug and Alcohol Screen ⁵	X	X																
COVID-19 Test	X																	
Biochemistry	X ⁶	X											X		X	X		
Haematology	X	X											X		X	X		
Urinalysis	X	X											X	X		X	X	
Coagulation ⁷	X	X											X		X	X		
Randomisation			X															
Adverse Events	X	X	X	X	X	X	X	X	X	X	X	X	X	X	X	X	X	
Vital Signs ⁸	X	X	X	X	X	X	X	X	X	X	X	X	X	X	X	X	X	
Physical Examination	X	X ¹¹														X ¹¹	X ¹¹	
12-Lead ECG ⁹	X	X	X	X	X						X		X	X		X	X	
Prior & Concomitant Medication	X	X	X	X	X	X	X	X	X	X	X	X	X	X	X	X	X	
Dose IMP ¹⁰				X														
Blood Sampling for PK			X		X	X	X	X	X	X	X	X	X	X	X	X	X	
Exploratory PD sample			X ¹²															

1. All cohorts will complete only 1 Treatment Period.
2. Participants will be in the clinical unit for their in-house period from the morning before dosing (Day -1), until the completion of all the assessments on Post-Treatment 3 (Day 4).
3. Eligibility will be determined during screening. Continued eligibility will be confirmed on Day -1, and pre-dose Day 1.
4. Height measured at Screening only.
5. A urine sample will be used to screen for drugs of abuse (including alcohol and cotinine).
6. Total serum testosterone only required at screening.
7. Coagulation testing INR, aPTT and PT.
8. Vital signs include the following assessments: supine systolic and diastolic blood pressure, supine heart rate, respiration rate and oral temperature
9. 12-lead ECG will be performed at screening, each period pre-dose and at 30 min, 4 h, 12 h, 24 h, 48 h and 72 h post-dose and at the post-study follow up visit.
10. IMP or placebo will be administered orally in a fasted state (after an overnight fast of at least 10 h) with 240 mL water. The fast will be broken 4 h post-dose with lunch.
11. Symptom directed
12. Cohort 3 onwards additional samples will be taken based on emerging data

Part B

Visits ^{1,2}	Screening	Treatment Periods 1 & 2														Follow up	
		In-house															
Days	Day - 28 to -2	Day - 1	Day 1										Post-Treatment 1 (Day 2)	Post-Treatment 2 (Day 3)	Post-Treatment 3 (Day 4)	5-7 days from last IMP dose	
Time (h)			Pre-Dose	0	0.5	0.75	1h	2h	3h	4h	6h	8h	12h	24h	36h	48h	72h
Informed Consent	X																
Inclusion/Exclusion ³	X	X	X														
Demographics	X																
Height/Weight/BMI ⁴	X	X															
Medical History & Concurrent Conditions		X															
Virology Tests (HIV, HBsAg, HCV)		X															
Drug and Alcohol Screen ⁵	X	X															
COVID-19 Test		X															
Biochemistry	X ⁶	X	X ⁶										X		X		X
Haematology	X	X											X		X		X
Urinalysis	X	X											X		X		X
Coagulation ⁷	X	X											X		X		X
Randomisation			X														
Adverse Events	X	X	X	X	X	X	X	X	X	X	X	X	X	X	X	X	X
Vital Signs ⁸	X	X	X		X	X	X	X	X	X	X	X	X	X	X	X	X
Physical Examination		X ¹¹													X ¹¹		X ¹¹
12-Lead ECG ⁹	X	X	X		X								X	X		X	X
Prior & Concomitant Medication	X	X	X	X	X	X	X	X	X	X	X	X	X	X	X	X	X
Dose IMP ¹⁰			X														
Blood Sampling for PK			X	X	X	X	X	X	X	X	X	X	X	X	X	X	

1. All cohorts will complete Treatment Period 1 & 2.
2. For Treatment Periods 1 & 2, participants will be in the clinical unit for their in-house period from the morning before dosing (Day -1), until the completion of all the assessments on Post-Treatment 3 (Day 4).
3. Eligibility will be determined during screening. Continued eligibility will be confirmed on Day -1, and pre-dose Day 1 for Treatment Periods 1 & 2.
4. Height measured at Screening only.
5. A urine sample will be used to screen for drugs of abuse (including alcohol and cotinine).
6. Total serum testosterone required at screening and pre-dose D1 each treatment period (Biochemistry sample: pre-dose Day 1 total serum testosterone only).
7. Coagulation testing INR, APTT and PT.
8. Vital signs include the following assessments: supine systolic and diastolic blood pressure, supine heart rate, respiration rate and oral temperature
9. 12-lead ECG will be performed at screening, each period pre-dose and at 30 min, 4 h, 12 h, 24 h, 48 h and 72 h post-dose and at the post-study follow up visit.
10. Participants will receive a single dose of AX-158 following an overnight fast of at least 10 h OR following consumption of a high-fat breakfast over 2 treatment periods (1 per period). AX-158 should be administered 30 mins after the start of the meal.
11. Symptom directed

Version:

Document Title:

Document Number:

Previous Document Number:

3.0

SAP Template - Phase 1

TEMP-00109

STATt008

Part C

Visits ¹	Screening	In-house															Follow up		
Days	Day - 28 to -2	Day - 1	Day 1-4, Day 10-13 ¹⁵														Day 5-9	5-7 days from last IMP dose	
Time (h)			Pre-Dose	0	0.5	0.75	1h	2h	3h	4h	6h	8h	12h	24h	36h	48h	72h		
Informed Consent	X																		
Inclusion/Exclusion ²	X	X	X																
Demographics	X																		
Height/Weight/BMI ³	X	X																	
Medical History & Concurrent Conditions	X																		
Virology Tests (HIV, HbsAg, HCV)	X																		
Drug and Alcohol Screen ⁴	X	X																	
COVID-19 Test		X																X ¹⁵	
Biochemistry	X ⁷	X	X ^{7,8}															X	X ^{6,7,8}
Haematology	X	X																X	X ⁶
Urinalysis	X	X																X	X ⁶
Coagulation ⁵	X	X																X	X ⁶
Randomisation			X																
Adverse Events	X	X	X	X	X	X	X	X	X	X	X	X	X	X	X	X	X	X	
Vital Signs ⁹	X	X	X	X	X	X	X	X	X	X	X	X	X	X	X	X	X	X ⁶	
Physical Examination	X	X ¹³																X ¹³	X ¹³
12-Lead ECG ¹⁰	X	X	X	X														X	X ⁶
Prior and Concomitant Medication	X	X	X	X	X	X	X	X	X	X	X	X	X	X	X	X	X	X	
Dose IMP ¹¹				X														X	X
Blood Sampling for PK				X	X	X	X	X	X	X	X	X	X	X	X	X	X	X ¹⁴	
Urine Sampling for PK				X ¹²															
Exploratory PD sample				X ¹⁶															

- For each cohort participants will be in the clinical unit for their inpatient visit from the morning before dosing (Day -1), until the completion of all assessments on Day 13.
- Eligibility will be determined during screening. Continued eligibility will be confirmed on Day -1, and pre-dose Day 1-10
- Height measured at Screening only.
- A urine sample will be used to screen for drugs of abuse (including alcohol and cotinine)
- Coagulation testing INR, aPTT and PT
- Pre dose on Day 5 only
- Total serum testosterone required at screening, fasted pre dose D1, D5 and on D11 (Biochemistry sample: pre-dose Day 1 total serum testosterone only)
- Serum LH required at pre dose D1, D5 and on D11 (Biochemistry sample: pre-dose Day 1 serum LH only)
- Vital signs include the following assessments: supine systolic and diastolic blood pressure, supine heart rate, respiration rate and oral temperature
- 12-lead ECG will be performed at screening, pre-dose and at 30 min, 4 h, 12 h, 24 h, 48 h and 72 h post-dose Days 1 and 10 and at the post-study follow up visit.
- For all cohorts IMP or placebo will be administered orally in a fasted state (after an overnight fast of at least 10 h) with 240 mL water. The fast will be broken 4 h post-dose with lunch on Days 1-10.
- Urine sampling: for AX-158: pre-dose and in intervals of 0-12, 12-24, 24-48 and 48-72 h post-dose on Day 1 and Day 10
- Symptom Directed
- Pre-dose trough sample day 5 only
- COVID-19 test on day 8 and prior to check out.
- Additional samples will be taken based on emerging data

3.5 SAMPLE SIZE CONSIDERATIONS

The sample size chosen for this study is not based on a formal statistical estimation but is considered adequate to meet the objectives of the study. A sufficient number of participants will be initially screened for enrolment to ensure that the planned sample size is achieved.

3.6 RANDOMISATION

Simbec-Orion using the PROC PLAN procedure of SAS® (9.4 or higher or EG). The randomisation code will include 2 dose-leaders (1 active:1 placebo) in each cohort (for Part A and Part C only).

Part A

Format and range of randomisation numbers: 101 – 156. Replacement subjects will be assigned the same randomisation as the participant they are replacing, however, 300 will be added to the number (i.e., 401 would replace 101 etc.).

The following IMPs will be used: AX-158 capsules vs Placebo.

Part B

Format and range of randomisation numbers: 201 – 208. Replacement subjects will be assigned the same randomisation as the participant they are replacing, however, 300 will be added to the number (i.e., 501 would replace 201 etc.).

The following IMPs will be used: AX-158 capsules in fed/faasted state.

Sequence	Period 1	Period 2
1	AX-158 - Fasted	AX-158 - Fed
2	AX-158 - Fed	AX-158 - Fasted

Part C

Format and range of randomisation numbers: 301 – 340. Replacement subjects will be assigned the same randomisation as the participant they are replacing, however, 300 will be added to the number (i.e., 601 would replace 301 etc.).

The following IMPs will be used: AX-158 capsules vs Placebo.

4 STUDY VARIABLES AND COVARIATES

4.1 PRIMARY VARIABLES

The primary safety endpoints for this study are as follows:

- Adverse events
- Laboratory safety parameters (biochemistry, hematology, coagulation, urinalysis)
- Vital signs (systolic/diastolic blood pressure, heart rate, oral body temperature and respiratory rate)
- 12-Lead ECG (Heart rate, PR interval, QRS width, RR interval, QT interval and QT interval corrected using Fredericia's formula (QTcF))

4.2 SECONDARY VARIABLES

The secondary plasma pharmacokinetic (PK) endpoints for this study are as follows:

- C_{\max} Maximum observed concentration

Version: 3.0
Document Title: SAP Template - Phase 1
Document Number: TEMP-00109
Previous Document Number: STATt008

• T_{max}	Time to maximum observed concentration
• T_{lag}	The delay in achieving T_{max} (only in Part B)
• k_{el}	Elimination rate constant
• $t_{1/2}$	Terminal elimination half-life
• AUC_{0-24}	Area under the concentration-time curve (AUC) from the time of dosing to 24 hour post dose
• $AUC_{0-\tau}$	If part C dosing is not q.d.
• AUC_{0-t}	Area under the concentration-time curve (AUC) from the time of dosing to the time of the last measurable concentration
• $AUC_{0-\infty}$	AUC extrapolated to infinity
• $AUC_{\% \text{ extrapolated}}$	Residual area
• CL/F	Apparent total body clearance
• Vz/F	Apparent volume of distribution

The secondary urine PK endpoints for Part C of this study are:

• A_e	Amount and cumulative amount of dose excreted in urine over each collection interval
• $A_e\%$	% and cumulative % of dose excreted in urine over each collection interval
• CL_R	Renal clearance

5 DEFINITIONS AND DERIVED VARIABLES

Treatment/IMP: Treatment or IMP is taken to mean either AX-158 at all dose levels, in the fed or fasted state, or placebo.

Baseline: For Part A and Part C unless stated otherwise, baseline is defined by subject and by variable as the last non-missing value (including repeat/unscheduled assessments) before the first dose of study drug.

For Part B unless stated otherwise, baseline is defined by subject and by variable as the last non-missing value (including repeat/unscheduled assessments) before the first dose of study drug in each treatment period. This will normally be the pre-dose assessment on Day 1 of each treatment period but if this assessment is missing (or not planned) then the last assessment prior to first dose in Period 1 will be used instead, if available. Specific baselines for each endpoint are defined in Section 11, where appropriate.

Study Day: Study day is the number of days since start of treatment where the date of first dose is counted as Day 1.

Blood Sampling Time Deviation: Actual sample time – planned sample time.

Protocol Deviation: a deviation related to study inclusion or exclusion criteria, conduct of the trial, subject management or subject assessment. This refers to any change, divergence, or departure from the study design or procedures defined in the protocol. Protocol deviations captured in the CRF will be discussed at the Data Review Meeting (DRM) before Database Lock (DBL). In addition, any deviations

identified during the DRM will be discussed and included in the database as necessary. All protocol deviations within the study database will be classified as either 'Major' or 'Minor' prior to DBL, details of which will be included within the Protocol Deviations listing.

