11.6.2 Laboratory Data

Routine safety clinical laboratory tests (biochemistry, hematology, coagulation, urinalysis) will be carried out at:

Part A: Screening, Day -1, 24h post dose, 72h post dose and at follow-up. An additional urinalysis test will be carried out at Day 1, 12h.

Part B: Screening, Day -1, 24h post dose, 72h post dose and at follow-up. An additional biochemistry test will be carried out at Day 1 pre dose (total serum testosterone only) and an additional urinalysis test will be carried out at Day 1 – 12h.

Part C: Screening, Day -1, 24h post dose, 72h post dose, pre-dose on Day 5 and at follow-up. An additional biochemistry test (total serum testosterone and LH only) will be carried out at Day 1 pre-dose, Day 5, Day 8 and Day 11 and an additional urinalysis test will be carried out at Day 1, 12h.

The laboratory parameters required for this study are listed in section 9.2.1.

Laboratory data listings will be presented in two ways:

- Out of range values - any values that fall outside of the normal/alert ranges based on the reference ranges provided by the Simbec-Orion Laboratory Services (presented in listing format within the data summaries)
- All safety laboratory data (including physician's review (Normal, Abnormal-NCS, Abnormal-CS)) with any out of range values flagged (presented within the data listings).

Descriptive statistics (N, n, mean, SD, minimum, median and maximum) of absolute and change from baseline (last assessment prior to first dose within a treatment period) values for each parameter at each protocol defined time point will be tabulated by treatment.

Microscopy, virology, COVID-19 test, urine drugs of abuse and alcohol screen and any unplanned laboratory parameters will also be listed.

If there are no further parameters databased other than those specified in section 9.2.1 then the 'Other Laboratory Data' listings should display, 'No other laboratory parameters to report'.

Laboratory data will be listed and summarised using the Safety Set.

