11.6.3 Vital Signs

Vital Signs will be recorded at:

Part A: Screening, Day -1, Day 1 pre-dose, 30 mins, 45 mins, 1h, 2h, 3h, 4h, 6h, 8h, 12h, 24h post dose, 36h post dose, 48h post dose, 72h post dose and follow-up.

Part B: Screening, Day -1, Day 1 pre-dose, 30 mins, 45 mins, 1h, 2h, 3h, 4h, 6h, 8h, 12h, 24h post dose, 36h post dose, 48h post dose, 72h post dose and follow-up.

Part C: Screening, Day -1, Day 1 and Day 10 at pre-dose, 30 mins, 45 mins, 1h, 2h, 3h, 4h, 6h, 8h, 12h, 24h post dose, 36h post dose, 48h post dose, 72h post dose, pre-dose on Day 5 and follow-up.

A window of \pm 10 min in relation to the nominal time-point is allowed.

Vital signs parameters (supine systolic and diastolic blood pressure and pulse rate, oral temperature and respiratory rate) will be listed with any out of normal range values (see Appendix 16.1) flagged (flag appended to relevant result). Descriptive statistics (N, n, mean, SD, minimum, median and maximum) of absolute and change from baseline (Day 1, pre-dose [of each treatment period for Part B] or last assessment prior to first dose, as applicable) values at each time point will be tabulated by treatment.

Vitals signs data will be listed and summarised using the Safety Set.

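### SAP Section 5 contradicts itself on the Part B baseline: when Day 1 pre-dose is missing or not planned, Period 2 falls back to a Period 1 value although a Period 2 Day -1 value is scheduled

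*SAP*

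**What the plan says.** SAP Section 5 gives a separate baseline rule for Part B. Its first sentence takes the last non-missing value "before the first dose of study drug in each treatment period". The next sentence expects this to be the Day 1 pre-dose assessment of each period, "but if this assessment is missing (or not planned"), "then the last assessment prior to first dose in Period 1 will be used instead". The paragraph opens with an allowance for other definitions and ends: "Specific baselines for each endpoint are defined in Section 11, where appropriate".

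Section 11 and the table shells then say the following.

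- **Laboratory data (11.6.2).** Change is taken from baseline defined as "change from baseline (last assessment prior to first dose within a treatment period"). The schedule is "Part B: Screening, Day -1, 24h post dose, 72h post dose and at follow-up", with one extra blood test at "Day 1 pre dose (total serum testosterone only"). The shell footnote of Table 14.3.2.5 refers only to the last available assessment before dosing and names no period.
- **Vital signs (11.6.3).** Baseline is Day 1 pre-dose of each period for Part B, "or last assessment prior to first dose, as applicable". The shell footnote of Table 14.3.3.1 is per-period.
- **ECG (11.6.4).** The text matches 11.6.3. The shell footnotes of Tables 14.3.4.1 and 14.3.4.2 refer to the last available assessment before dosing and name no period.

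The laboratory, vital signs and ECG shells are all to be repeated for Part B.

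**The concern.** The two Section 5 sentences cannot both be applied to Period 2. When the Period 2 Day 1 pre-dose value is absent, the first sentence leads to Day -1 of Period 2, which is scheduled. The second passes over that value and goes back to before the first dose of the study.

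A Period 2 change measured from a Period 1 baseline is no longer the change over Period 2. It also contains whatever happened during Period 1 dosing and the washout. These measurements are listed as primary safety variables in SAP Section 4.1. Two programmers working from the same SAP could derive different baselines for the same participant, and the difference would not show in the output.

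**Working it through.** **1. Is there a same-period value to fall back on?** Yes. The SAP's Part B schedule covers Treatment Periods 1 and 2 under one set of columns, includes Day -1, and has participants resident from the morning before dosing in both periods. The blood volumes in Protocol Table 10.9.5 agree:

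- Laboratory samples after screening: 3 per period (Day -1, 24 h, 72 h) × 2 periods + 1 follow-up = 7.
- Biochemistry: 7 × 4.5 mL = 31.5 mL. Haematology: 7 × 3.0 = 21 mL. Coagulation: 7 × 2.7 = 18.9 mL. All three match the table.
- Total: 4.5 + 31.5 + 3.0 + 21 + 2.7 + 18.9 + 112 = 193.6 mL, the table's figure.

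The count of three per period requires a Day -1 laboratory sample in Period 2. Sections 11.6.3 and 11.6.4 also schedule vital signs and ECG on Day -1 in Part B.

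**2. Which value does each rule choose for Period 2?** Doses are at least 7 days apart, extendable to 14 (Protocol 10.1 and 10.2). Count days from the Period 1 dose as day 0, so the Period 2 dose falls on day 7 or day 14.

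| Rule | Laboratory value chosen | Days before Period 2 dose, 7-day gap | 14-day gap |
|---|---|---|---|
| Section 5, first sentence; 11.6.2 | Period 2 Day -1 | 7 − 6 = 1 | 14 − 13 = 1 |
| Section 5, fallback | Period 1 Day -1 | 7 − (−1) = 8 | 14 − (−1) = 15 |

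For vital signs and ECG the Period 1 value would normally be Day 1 pre-dose, so the fallback would be about 7 or 14 days old. In Period 1 the rules agree, so only Period 2 is affected.

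**3. When does the fallback apply?**

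- Haematology, coagulation and biochemistry other than testosterone have no planned Day 1 pre-dose sample. Read literally, Section 5 sends every participant's Period 2 laboratory baseline to Period 1.
- Vital signs, ECG and testosterone are planned at Day 1 pre-dose in each period. The fallback applies only if that value is missing.

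**4. What does the wrong baseline do?** Let Y2 be a Period 2 post-dose value, B1 the Period 1 baseline and B2 the Period 2 baseline. Then Y2 − B1 = (Y2 − B2) + (B2 − B1). The error is B2 − B1, the participant's shift between the two periods' baselines. A QTcF change moves to another category if that shift carries it across 0, 30 or 60 ms, the boundaries in 11.6.4. The documents give no between-period variability or expected missing rate, so the number of values moved cannot be calculated.

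**The case against.** The strongest reply is that the SAP states its own order of precedence. Section 5 is a general rule that yields to Section 11, and 11.6.2 is per-period, so no laboratory baseline should go back to Period 1. This stands. A reader might infer that all Period 2 laboratory changes will be wrong, but the documents support that only if the programmer ignores the deferral. What survives is a risk of misreading. Laboratory panels are the main tabulated Part B data with no planned Day 1 pre-dose assessment. If 11.6.2 always prevails, the words about unplanned assessments have almost nothing to govern, and a programmer could reasonably think they were written for laboratory data.

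For vital signs, the Table 14.3.3.1 footnote already gives the per-period rule. That also stands, although the 11.6.3 text is looser than the footnote. For ECG neither the text nor the shell settles the matter. The event needed is a missing pre-dose ECG in a resident participant, which should be uncommon.

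A reader might also infer that the fallback confounds fed with fasted. Part B is a two-sequence crossover. If the sequences are split 4:4 (an assumption, since no split is given), half of each treatment's observations fall in Period 2. A common shift d applied to all Period 2 values moves each treatment mean by 4d/8 = d/2, and the difference by d/2 − d/2 = 0. Sporadic missing values or unequal sequences could leave a small imbalance. No formal safety comparison of fed with fasted is planned, and the primary safety objective names Parts A and C.

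Finally, a Period 1 value is defensible as a last resort. If a participant has no pre-dose value at all in Period 2, the last non-missing value before that dose would be a Period 1 post-dose measurement. A value from before any exposure may be preferable to that.

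**Conclusion.** The conflict within Section 5 is real and can be shown from the text alone. For Period 2 the fallback replaces a scheduled value about 1 day old with one from before any AX-158 exposure. For laboratory tests that value is about 8 to 15 days old.

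The practical reach is small. If 11.6.2 is followed, laboratory data are unaffected. If Section 5 is programmed literally, Period 2 changes for all of the up to 8 participants are affected, testosterone excepted. For ECG, the exposure is a missing Period 2 pre-dose recording, which could alter that participant's change value or QTcF-change category. For vital signs the same applies if Section 5 is followed instead of the shell. The effect falls on individual and mean Period 2 changes in descriptive tables. General confounding of fed with fasted is not supported. This is a minor point, worth correcting because the correction is so small.

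One limit applies. The SAP was written against protocol version 5.0 and the protocol available is version 4.0. The conclusion does not depend on the difference, because the SAP's own Part B schedule shows Day -1 assessments under both periods.

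**What to change.** In SAP Section 5, make the Part B fallback the last assessment before dosing in the same treatment period. Allow a Period 1 pre-dose value only when no same-period value exists, and flag it in the listing and in a table footnote.

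Carry the same limit into 11.6.3 and 11.6.4, and into the laboratory and ECG shell footnotes (Tables 14.3.2.5 to 14.3.2.7, 14.3.4.1 and 14.3.4.2). Section 11.6.2 and the Table 14.3.3.1 footnote already read as needed and can serve as the model.

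The cost is a few words in each place, plus a flag in the derivation. No new data are needed. Because the last resort is kept, no participant loses a baseline that the present rule would supply.
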